6.7. Safety

The distinction between the primary/secondary outcomes and safety outcomes is not as clear in this trial as it would be in a typical clinical trial of a novel therapeutic agent. Many outcomes that would typically be considered potential adverse consequences or safety outcomes will be analyzed similarly as the secondary outcomes. For example, the other tobacco product use will be analyzed using similar statistical methods as for the other continuous primary/secondary endpoints.

AEs and SAEs will be recorded as described in the Adverse Event SOP. AEs and SAEs will be tabulated and compared across treatment groups. Count of AEs will be analyzed using Poisson regression or negative binomial regression as described in Section 6.4.

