16.6.7. Safety

The distinction between the primary/secondary outcomes and safety outcomes is not as clear in this trial as it would be in a typical clinical trial of a novel therapeutic agent. Many outcomes that would typically be considered potential adverse consequences or safety outcomes will be analyzed similarly as the secondary outcomes. For example, the other tobacco product use will be analyzed using similar statistical methods as for the other continuous primary/secondary endpoints.

AEs and SAEs will be recorded as described in the Adverse Event SOP. AEs and SAEs will be tabulated and compared across treatment groups. Count of AEs will be analyzed using Poisson regression or negative binomial regression as described in Secondary Endpoint Analysis.

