3.2. Sample Size

Sample size was re-estimated for this project by [name] on 8/21/2019. After discussion with members of the CENIC External Advisory Board and representatives of the National Institute of Drug Abuse and Food and Drug Administration, we changed the sample size from 700 to 500.

More power analysis was performed on 11/10/2021 for 2 smaller sample sizes (N = 450 and 400), with all the other parameters being the same as the power analysis performed on 8/21/2019.

We will enroll at least 400 rather than the 700 subjects originally proposed (200 per group) to the study and assume a 20% attrition rate over the 12-week post randomization period. Power analysis was performed for two of the primary outcomes in the primary aim: CPD smoked at the end of Phase 3 and smoke-free days during Phase 3.

3.2.1 Methods: See Section 6.9 for interim analysis and the methods for the sample size re-estimation.

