6.3.2. Secondary Analysis

For the Week 12 CPD and total number of smoke-free days, we will perform an adjusted analysis, adjusting for baseline value, study site (the randomization stratification factor), whether the Week 12 visit is pre-COVID or not, and any baseline characteristics (listed in Section 6.2) which are different at $p<0.20$, in multivariable regressions to improve efficiency.

For the CPD outcome measured repeatedly, we will use linear mixed effects models (Verbeke and Molenberghs, 2000). Fixed effects in the model will include: treatment group, visit, treatment group by visit interaction, baseline CPD, study site, whether the visit time is pre-COVID or not (as a time-dependent covariate), and any baseline characteristics (listed in Section 6.2) which are different at $p<0.20$. A random intercept for each subject will also be included in the model to account for within subject correlation.

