6.4. Secondary Endpoint Analysis

The secondary endpoints will first be summarized by treatment group using mean and standard deviation. We will use similar adjusted regression methods for the secondary endpoints as for the primary endpoints described in Section 6.3.2. Details are described as follows.

- For the percent change (relative to the measure at the end of Phase 2) of the biomarker measured repeatedly (weeks 4, 8, 12), we will use linear mixed effects models (Verbeke and Molenberghs, 2000). Fixed effects in the model will include: treatment group, visit, treatment group by visit interaction, study site, whether the visit time is pre-COVID or not (as a time-dependent covariate), and any baseline characteristics (listed in Section 6.2) which are different at $p<0.20$. A random intercept for each subject will also be included in the model to account for within subject correlation.
- For study cigarette smoked, similar analyses to total cigarettes per day will be performed.
- For the abstinence outcome, we will use logistic regression.

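### The AE count model in SAP 6.7 and protocol 16.6.7 states no exposure time, so unequal dropout would bias the comparison of arms

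*Combined protocol and SAP*

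**What the plan says.** SAP 6.7 has AEs and SAEs tabulated and compared between arms, without naming a denominator, and then says: "Count of AEs will be analyzed using Poisson regression or negative binomial regression as described in Section 6.4". Protocol 16.6.7 has the twin sentence: "Count of AEs will be analyzed using Poisson regression or negative binomial regression as described in Secondary Endpoint Analysis".

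SAP 6.4 describes three analyses: a linear mixed model for the biomarker; for study cigarettes, "For study cigarette smoked, similar analyses to total cigarettes per day will be performed"; and "For the abstinence outcome, we will use logistic regression". None is a count model. Protocol 16.6.4 has the same content. SAP 6.4 also opens with a general pointer: "We will use similar adjusted regression methods for the secondary endpoints as for the primary endpoints described in Section 6.3.2". Section 6.3.2 in turn says "For the Week 12 CPD and total number of smoke-free days, we will perform an adjusted analysis, adjusting for baseline value", followed by site, COVID period and unbalanced baseline characteristics. It names no model family. On this route the Poisson or negative binomial family is first named in 6.3.1, for smoke-free days. SAP 6.5 names it again for days of non-combusted product use. No offset is written in either place.

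On observation time, SAP 3.2 says the plan will "assume a 20% attrition rate over the 12-week post randomization period". Protocol 13.1 has AEs assessed at every study visit. These assessments start at the baseline visits (protocol 5.2.2) and run to the week 16 visit, whose window is -7 to +30 days (protocol 5.6.1). SAP 6.8 gives specific rules for missing IVR days and biomarkers, and none for AE counts after dropout.

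**The concern.** The outcome in the AE model is a number of events collected over a period that differs between participants. A participant who leaves at week 4 has had a quarter of the time to report an AE that a participant seen at week 16 has had. A Poisson or negative binomial model without an exposure term compares mean counts, not rates. If mean time observed differs between arms, that difference passes straight into the estimated ratio.

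What is at stake is the only model the plan specifies for AE counts, in a trial meant to inform nicotine regulation. The arm with more dropout would appear to have fewer AEs than its true rate implies. If the exposure term is settled only after attrition by arm is known, the safety analysis becomes dependent on the data.

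**Working it through.** **The plan's own figure.** The documents give no AE rate, expected AE count or AE power, so there is nothing to reproduce.

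**Inputs.** Allocation is 1:1 (SAP 3.1). Overall attrition is 20% (SAP 3.2). Follow-up runs to week 16 (protocol 5.6.1). The following are assumptions, because the documents do not give them: dropout by arm (d), the mean week at which dropouts leave (t), and an AE rate that is constant over time.

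**Formula.** Mean weeks observed in an arm is M = (1 − d) × 16 + d × t. With a constant rate and true rate ratio R (VLNC/NNC), a model with no offset estimates R × M(VLNC) / M(NNC). The second factor is the bias.

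**Results, with dropout averaging 20% over the two arms.**

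| Dropout VLNC / NNC | t = 8 weeks | t = 4 weeks |
|---|---|---|
| 20% / 20% | 14.4 / 14.4 = 1.000 (0%) | 13.6 / 13.6 = 1.000 (0%) |
| 22% / 18% | 14.24 / 14.56 = 0.978 (2%) | 13.36 / 13.84 = 0.965 (3%) |
| 25% / 15% | 14.0 / 14.8 = 0.946 (5%) | 13.0 / 14.2 = 0.915 (8%) |
| 30% / 10% | 13.6 / 15.2 = 0.895 (11%) | 12.4 / 14.8 = 0.838 (16%) |

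The higher dropout is placed in the VLNC arm for illustration only. Swapping the arms inverts the ratios.

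**Sensitivity to the window.** The plan does not define the period over which AEs are counted. Over 12 weeks, 25% / 15% gives 10.5 / 11.1 = 0.946 at t = 6 and 10.0 / 10.8 = 0.926 at t = 4, a bias of 5% to 7%. Completers vary too: the week 16 window runs from 16 − 1 = 15 weeks to 16 + 30/7 = 20.3 weeks.

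**Simulation.** Negative binomial counts were generated with 200 per arm, a mean of 2 AEs per person over full follow-up and dispersion 1 (both assumed), using 600 runs per setting. Dropout times were uniform over all of follow-up, or over its first half. Models were fitted with and without log(exposure) as offset, with dispersion held at its true value.

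- True ratio 1.0, no offset: 0.943 (uniform) and 0.917 (early) at 25% / 15%; 0.895 and 0.842 at 30% / 10%. These agree with the formula.
- True ratio 1.3, no offset: 1.23 and 1.20 at 25% / 15%; 1.17 and 1.09 at 30% / 10%.
- With the offset: 1.00 and 1.30–1.31 in every setting.
- Rejection at nominal 5% under a true ratio of 1.0, no offset: 8.2% and 13.2% at 25% / 15%; 16.7% and 28.8% at 30% / 10%. With the offset it was 3.7% to 5.8% in all settings.

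The simulation standard error near 5% is √(0.05 × 0.95 / 600) = 0.9 points. Without the offset, rejection was already 6.7% to 7.2% at equal dropout. A small part of the excess therefore comes from fixing the dispersion while exposure varies, and not from bias.

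**The case against.** **The plan does not rule out an offset.** It is silent, and the team uses observed-time denominators elsewhere: SAP 6.9.1 divides smoke-free days by total IVR days, and SAP 6.3 frames that endpoint as days out of the Phase 3 total. AE recording is also deferred to an Adverse Event SOP that is not in the documents. This stands. The point is an under-specification, and a reader who infers that the sponsor has chosen a wrong model goes beyond the text.

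**The reference can be followed.** SAP 6.7 itself names the model family, and the route from 6.4 to 6.3.2 to 6.3.1 reaches a count model, an over-dispersion rule and a covariate list that includes site. This largely stands, and that half of the point is mainly editorial. The route still supplies no exposure term, and its baseline-value covariate has no stated AE counterpart.

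**Unequal dropout is not shown.** No document gives attrition by arm. SAP 6.8 provides for missingness associated with arm, but only as a possibility. Protocol 5.5 expects less non-compliance in the NNC arm, but that concerns product use and not dropout. This stands, and the range must start at 0%.

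**The AE rate may not be constant.** The randomisation text in protocol 5.2.4 expects experimentation with products mostly in the first weeks. If AEs cluster early, those who leave have already passed much of their risk. The bias is then smaller than computed, and an offset could overcorrect. If AEs cause dropout, an offset does not remove the informative censoring. Both limits stand.

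**AEs up to exit are partly captured.** Early-termination visits include an AE assessment (protocol 13.4), and participants who leave because of an AE are followed (protocol 13.1). This secures events up to exit if the visit is attended. Follow-up after exit is described for the existing problem, not as continued collection of new AEs, so the difference in time at risk remains.

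**Conclusion.** The point holds as a minor gap in the safety analysis. Read literally, the AE count model has no exposure term and its reference leads to a section without a count model. The resulting bias is zero if time observed is equal in the two arms. Otherwise it is about 2–3% at 22% / 18% dropout, 5–8% at 25% / 15% and 11–16% at 30% / 10%. Those figures rest on a constant AE rate, a 16-week window, 20% dropout overall, and dropouts leaving on average between weeks 4 and 8.

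A reader might infer that VLNC cigarettes will look safer than they are. The documents do not support that: they predict neither the direction nor the size of any difference in dropout, and the bias would run the other way if the NNC arm lost more participants. The primary and secondary endpoints and their power are not affected.

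**What to change.** In SAP 6.7 and protocol 16.6.7:

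1. Define the AE observation period as randomisation to the participant's last AE assessment.
2. State the model in place: Poisson, or negative binomial if over-dispersed, with log(time observed) as offset. List the covariates directly, because the baseline value in 6.3.2 has no AE counterpart. Site is already implied there.
3. Report AE rates per person-time by arm beside the planned tabulation.
4. Show the proportion of participants with at least one AE by arm, because the offset assumes a roughly constant rate and does not correct for informative dropout.
5. Replace the reference to SAP 6.4 (protocol 16.6.4) with this text.

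Robust standard errors are optional, since the negative binomial model already allows for over-dispersion. The cost is a few sentences and one model term, using visit dates that are already collected. No new data are needed and the sample size does not change.

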6.8. Missing Data

Every effort will be made to limit the amount of missing data in this trial. Study participants will be incentivized to attend study sessions and complete the daily IVR as detailed in the study protocol (Participate Compensation subsection). However, some level of missing data is inevitable in a study of this kind. We will compare subjects who do and do not complete the study in order to identify baseline covariates associated with study completion.

We will use multiple imputation with the Markov Chain Monte Carlo (MCMC) method (Schafer, 1997; Little and Rubin, 2002), carried out in PROC MI in SAS. If the treatment group is associated with missing values, we will conduct multiple imputation for each treatment group separately (Molenberghs and Kenward, 2007). At least 10 imputed data will be generated, with the treatment effect being assessed in each imputed data set. A final single assessment of treatment arm difference will be obtained from combining the results across the imputed datasets using PROC MIANALYZE in SAS.

We will then conduct sensitivity analyses of primary and secondary endpoints by baseline imputation and the last observation carried forward (LOCF) method. Specifically, for the baseline imputation method, for a day with missing IVR data, the Phase 2 mean CPD will be imputed and non-abstinence will be assumed. For the outcome of biomarkers, missing data will be replaced by baseline values (i.e., no change in biomarkers). This will serve as a “worse-case scenario” as treatment group will be, on average, balanced at baseline. The results of these analyses will be compared to the primary analysis to evaluate the robustness of our conclusions.

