4.1. Intent-to-Treat

The primary analysis of all endpoints will adhere to the intent-to-treat principle. Under this principle, all randomized subjects will be included in the analysis in the group to which they were randomized regardless of protocol violations and compliance to treatment assignment.

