5.1. Primary Endpoints

- Cigarettes per day (CPD): the mean cigarettes (study and non-study cigarettes) smoked per day based on 7 days' Daily Interactive Voice Response (IVR)-Revised (corrected with participant for errors) data before the week 12 visit.
- Smoke-free days during Phase 3: the number of days not smoking any combustible products based on IVR-Revised.

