5.2. Secondary Endpoints

- Biomarker: percent change in biomarker, CEMA, at the weeks 4, 8 and 12 visits during Phase 3 as compared to the last visit in Phase 2.
- Study cigarettes per day (CPD): the mean of study cigarettes smoked per day based on 7 days' Daily IVR-Revised data before the week 12 visit.
- Seven-day abstinence: if total CPD=0 for all 7 days before the week 12 visit and CO \leq 6ppm at week 12.

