6.3.1. Primary Analysis

We expect the two groups to, on average, be balanced for important baseline characteristics due to randomization, so the primary analyses will be regressions for the difference in CPD and the number of smoke-free days between two conditions, adjusting for only the baseline value (the mean CPD and the percent of smoke-free days during Phase 2, respectively). Specifically, for the CPD outcome at week 12, we will use linear regression; for the number of smoke-free days, we will use Poisson regression or negative binomial regression when there is over-dispersion in the count data.

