6.9. Interim Analyses

6.9.1. Interim Analysis for Sample Size Re-estimation (see above)

One interim analysis was conducted for sample size re-estimation. Nuisance parameters were estimated based on non-comparative data, whereas the significance level, the desired power, and the assumed targeted difference in outcome due to treatment assignment were not changed. In general, sample size re-estimations based on non-comparative data are expected to have a negligible effect on the Type I error (USDHHS, FDA, CDER, and CBER, 2018).

First, we calculated the distribution of gender and age (18-24, 25-44, and ≥ 45 years old). For the outcome of CPD, we calculated the variance for the pooled sample. For the outcome of cigarette abstinence, we evaluated the control (NNC) group’s average rate of abstinence, which is calculated as the total number of smoke-free days observed among randomized participants divided by the total number of IVR days during Phase 3 (12 weeks).

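### SAP 6.8 gives its normal-model imputation no unit or conversion rule for smoke-free days and abstinence, and ties by-arm imputation to the wrong condition

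*Combined protocol and SAP*

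**What the plan says.** SAP 6.8 and protocol 16.6.8 state the main method in near-identical words: "We will use multiple imputation with the Markov Chain Monte Carlo (MCMC) method", with at least 10 imputations pooled in PROC MIANALYZE. On treatment arm, SAP 6.8 says: "If the treatment group is associated with missing values, we will conduct multiple imputation for each treatment group separately". For this main method neither section names the imputed unit (day, week, 84-day total or indicator), the variables in the imputation model, or any rounding, bounding or threshold rule. A day-level unit and a rule for abstinence appear only for the baseline-imputation sensitivity analysis.

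The imputed data must then enter these models:

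- SAP 6.3.1: "for the number of smoke-free days, we will use Poisson regression or negative binomial regression when there is over-dispersion in the count data". SAP 5.1 defines the endpoint as "the number of days not smoking any combustible products based on IVR-Revised".
- SAP 6.4: "For the abstinence outcome, we will use logistic regression". SAP 5.2 counts a participant as abstinent "if total CPD=0 for all 7 days before the week 12 visit", with CO at or below 6 ppm at week 12.
- SAP 4.1: "all randomized subjects will be included in the analysis in the group to which they were randomized".

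**The concern.** MCMC in PROC MI draws from a multivariate normal model. That suits week-12 CPD, study CPD and CEMA change. It does not suit a count with a low mean, or an indicator that depends on exact zeros. Someone has to decide how a draw of -3.4 smoke-free days, or of 0.3 cigarettes on a day, is to be used. Dropping participants whose imputed total is negative would conflict with SAP 4.1. The trial is open label, so a rule chosen after data are in hand has no blinding to protect it.

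The arm condition is a second problem. Arm belongs in the imputation model because it is expected to predict the outcome; SAP 3.2.3 assumes 7 versus 15 CPD and an 11-day difference. Whether arm also predicts missingness is a different question. If the condition is not met and the pooled model leaves arm out, missing values in both arms are drawn towards a common mean and the treatment effect shrinks. The plan gives no test or level for the association.

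**Working it through.** **Inputs.** SAP 3.2: at least 400 enrolled, 20% attrition. SAP Table 1: CPD SD 9.62, NNC smoke-free rate 5.04%. SAP 3.2.3: 7 versus 15 CPD, 11-day difference over 84 days, alpha 0.025 two-sided (critical value 2.24). The documents give no SD for smoke-free days, so a range is used.

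**1. The plan's own power.** n = 400 × 0.8 / 2 = 160 per arm. Rates are 0.0504 and 0.0504 + 11/84 = 0.1814. z = 0.1310 / √((0.0504 + 0.1814)/160) = 0.1310 / 0.0381 = 3.44. Power = Φ(3.44 − 2.24) = 0.885, against 0.88 stated. N = 450 and 500 give 0.920 and 0.946 (stated 0.92 and 0.94), and CPD power exceeds 0.99. The arithmetic is sound.

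**2. Do the draws fit the models?** Mean smoke-free days: NNC 0.0504 × 84 = 4.23; VLNC 4.23 + 11 = 15.23. P(draw < 0) = Φ(−mean/SD). For an assumed SD of 8 to 20 days this is 30% to 42% in NNC and 3% to 22% in VLNC (2% in NNC if the counts were purely Poisson). In a simulation with an NNC SD of about 13 days, 31% of all draws were negative. On raw draws a logistic fit was refused, a negative binomial fit did not converge, and a Poisson fit ran although the values were not counts. Rounding and truncating to 0-84 raised the mean of NNC draws from 4.2 to 7.5 days. For daily CPD, none of 11.0 million simulated draws equalled zero, so no imputed day can meet the abstinence definition without a threshold.

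**3. Effect of the unstated choices.** Assumptions: 200 per arm; 20% dropout, with dropouts keeping 0-11 weeks (6.5/12 × 20% = 10.8% of days missing); observed weeks used; beta-binomial days with within-person correlation 0.2/0.4/0.6; 10 imputations; 300 trials (200 for the daily row). The full-data VLNC:NNC ratio is about 3.6.

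| Imputation | Change in ratio, % (0.2/0.4/0.6) |
|---|---|
| Weekly, by arm, unbounded | +0.2 / −0.2 / +0.2 |
| Weekly, by arm, floored and rounded | −1.9 / −2.6 / −2.1 |
| Daily CPD, by arm, rounded | +2.4 / +1.9 / +2.1 |
| Weekly, arm omitted | −4.5 / −3.9 / −3.0 |
| Weekly, arm omitted and floored | −7.1 / −7.2 / −6.6 |
| Weekly predictive mean matching, by arm | −0.6 / −0.1 / +1.1 |

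The Monte Carlo SE of the weekly rows is 0.2-0.3%. With rounded daily draws the arm difference in 7-day abstinence goes from 0.34 to 0.37, 1.82 to 1.57 and 4.66 to 4.03 percentage points.

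**4. Arm omitted.** If a fraction m of whole endpoint values is imputed from a pooled mean, each arm mean becomes (1 − m) × arm mean + m × pooled mean, and the difference becomes (1 − m) × d. At m = 0.2: 0.8 × 11 = 8.8 days and 0.8 × 8 = 6.4 CPD. The pooled mean is 9.73, so the arm means are 0.8 × 4.23 + 0.2 × 9.73 = 5.33 and 0.8 × 15.23 + 0.2 × 9.73 = 14.13, and the ratio falls from 3.60 to 2.65. If observed weeks are used, the CPD difference at weekly correlation 0.6/0.8/0.9 goes from 8.08/8.10/7.99 to 7.74/7.85/7.80, which is 2-4% smaller.

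**5. How often would the condition be met?** If it were tested at two-sided 0.05 (assumed) with 200 per arm: in 5% of trials at 20%/20% dropout, 17% at 22%/18%, and 71% at 25%/15%.

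**6. Effect on the test.** In the weekly simulations of step 3 every method rejected in 100% of trials at the planned effect. At a smaller effect with about 80% power, rejection changed by about 3 points at most. For whole-value dilution, 8.8 days in step 1's formula gives power 0.752 with the NNC rate held at 5.04% (0.70 with the diluted NNC rate, 0.1048/0.0381 = 2.75). That formula is pessimistic: it implies a VLNC SD of 84 × √0.1814 = 35.8 days, above the maximum for a 0-84 outcome with mean 15.23, √(15.23 × 68.77) = 32.4. CPD power at 6.4 stays above 0.99.

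**The case against.** A reader might infer that the draws cannot be used and the primary analysis cannot be run. The documents do not support that. Rounding, bounding or thresholding would let the draws enter the models, and nothing in the SAP forbids it. What stands is that a rule must be added, that none is planned, and that plausible rules move the ratio in opposite directions.

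A reader might also infer that the plan omits arm from pooled imputation. It says only when imputation is split by arm and is otherwise silent, so dilution is a risk and not a stated step. Likewise, the SAP uses neither the term multivariate normal nor the words all endpoints: the first follows from the named method, the second from an unrestricted paragraph. Of the five primary and secondary endpoints, three are continuous and have no conversion problem.

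The plan also has safeguards. Missed calls are repaired by Timeline Followback (protocol 5.2.1), early-termination visits collect it again (protocol 13.4), and the baseline-imputation sensitivity analysis yields valid counts. These limit the harm. They do not recover the days after a participant leaves, within the 20% attrition that the plan assumes, and a sensitivity analysis does not complete the primary method.

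Finally, the step 3 shifts are under half a standard error of the log ratio, and a reader might take that as a ceiling. It holds only if dropouts' observed weeks are used, which the SAP does not say.

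**Conclusion.** The point holds in two parts. First, the only main imputation method does not match the planned models for one primary endpoint (smoke-free days) and one secondary endpoint (7-day abstinence) without an ad hoc rule that itself shifts the estimate. Second, the condition for imputing by arm is the wrong one, because it asks about missingness when the reason to use arm is the outcome. If arm is left out, both primary effects are diluted even with equal dropout.

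The size of the dilution depends on the unstated unit. It runs from about 2-4% (CPD difference) and 3-4.5% (smoke-free-day ratio), with observed Phase 3 weeks used, up to the full missing fraction if whole endpoint values are imputed. The smoke-free-day figures also rest on assumed within-person correlations. The stronger inference that the trial's overall conclusion would reverse is not supported at the planned effect. What is at stake is avoidable bias in the reported estimates and a primary method that two analysts could carry out differently. It should be fixed before analysis.

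**What to change.** In SAP 6.8 and protocol 16.6.8:

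1. Always impute separately by arm, and delete the condition about association with missing values.
2. For smoke-free days and abstinence, replace MCMC with PROC MI FCS at a stated unit: for example, predictive mean matching of weekly smoke-free-day counts, or logistic imputation of single missing days. Use the Phase 2 value, site and earlier Phase 3 data as predictors, and add the observed days to form the Phase 3 total.
3. Derive 7-day abstinence by SAP 5.2's own definition: imputed total CPD of zero on all 7 days and CO at or below 6 ppm, with CO imputed in the same FCS model. The method for daily CPD must be able to return an exact zero; predictive mean matching can. Do not derive abstinence from a smoke-free-day count of 7. Smoke-free days exclude any combustible product, while abstinence is defined on cigarettes plus CO, so that shortcut would change the endpoint.

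Keep baseline imputation and LOCF as sensitivity analyses. The cost is wording in two documents, a different statement in the same SAS procedure, and some extra programming and run time. No new data are needed.
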